Page 7 of 33 Version: 1.0, 8/22/2022 **Primary objective**: To assess the role of malaria as significant contributor to death in adults (ages 18 years and above) in disease endemic settings in sub-Saharan Africa and South Asia.

Secondary objectives:

- To assess the relative contribution of other infectious and non-infectious disease etiologies to death in adults 18 years and above
- 2. To identify the etiology of enrolled non-malarial adult deaths
- 3. To assess the prevalence of SARS-CoV-2 positivity among enrolled deaths
- 4. To characterize anti-microbial and anti-malarial sensitivity patterns in settings with limited routine culture and sensitivity testing
- 5. To describe the differences in mortality rates attributed to malaria and other infectious and non-infectious disease etiologies in rural vs urban settings

3. Background

Malaria

In Sub-Saharan Africa and South Asia, malaria is recognized as a major cause of preventable mortality among children and pregnant women, the two populations traditionally considered vulnerable to severe disease. In such settings, and where transmission intensity remains high, continuous exposure to the infective bites of anopheles mosquitoes and infections with infectious disease agents contributes to the progressive acquisition of partial natural immunity against majority of these infections. For example, this natural immunity is the basis for the clinical tolerance to malarial infections that older children, teenagers, and adults experience. For this reason, very few clinicians practicing in malaria-endemic settings argue that malaria represents a substantial cause of mortality among adults. However, epidemiological studies using the verbal autopsy tool as the method to infer cause of death have highlighted that malaria appears to be an important contributor to adult mortality (15-20% in some age groups). While verbal autopsies have repeatedly shown poor precision in determining cause of death at the individual level, the potential role of malaria as a cause of mortality in adults remains to be poorly described especially in malaria-endemic populations.

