awarded for July 2019 through June 2025 to support the implementation of Phase 2 CHAMPS network activities. The primary objectives for Phase 2 included (1) continuing to generate and analyze data that characterizes the specific causes and contributors to child mortality, (2) ensuring that individuals, communities, national and global stakeholders have the skills and tools to use CHAMPS data; (3) to drive actions to reduce child mortality, and (4) strengthening network capabilities with infrastructure and tools to achieve program priorities and actions.

We propose to add a study in the context of the existing CHAMPS project to unequivocally respond to a controversial finding by several epidemiological studies (using the verbal autopsy tool as the method to infer cause of death) that malaria appears to be an important contributor to adult mortality, with a classical "U" shaped curve, according to age. We propose to conduct a set of MITS in community and hospital adult deaths to refute or confirm the hypothesis that malaria is a significant contributor to adult mortality. CHAMPS network sites aim to conduct 200-300 MITS (10-20% community deaths, 80-90% hospital deaths) at their respective site among individuals having any cause other than trauma as part of the process that led to their death (i.e., not limited to those with fever).

Social behavioral science (SBS)

Although significant amount of foundational work has been done by the CHAMPS network at each of the sites since 2015, site investigators will conduct a rapid assessment to understand community acceptance and expectation with conducting MITS in recently deceased adults. These SBS activities are covered under separate protocols at each site but a brief description is included below. Data will not be received by the Program Office at Emory University.

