- 6. Occupational Health Care: All study personnel will be required to undergo medical follow-up. These will include vaccination for hepatitis B, Influenza, tetanus and pertussis. Regular COVID-19 testing will be performed as defined by national guidelines and those who test positive will undergo isolation as defined by national guidelines. Personnel will receive regular grief counselling and debrief. They will be encouraged to maintain social distancing and adhere to COVID-19 prevention regulations

7. Statistical Analysis Plan

Sample size determination

Our sample size determination method was adopted from a method which has been detailed elsewhere.²⁴ In brief, below is our sample size estimates:

 $n=(Nz^2p(1-p)/((N-1) d^2+z^2p(1-p))$

n = minimum sample size

N = Number of adult mortalities, per year (32,000)

Z = z value 1.96 at 5% type 1 error, 95% confidence level

p = prevalence of adult respiratory disease mortality (estimated at 15% of all adult mortalities)

d = margin of error taken as 0.05

The minimum sample size needed for respiratory disease mortality is 195. The estimated prevalence of adult malaria mortality is 10-14% per site, which will require a smaller target sample size (n=138 at 10% prevalence). This study plans to enroll 200 or more adults at each site.

Interim analysis

A preliminary evaluation of data will be conducted by each site after 25-50 deaths with completed MITS. Case demographics and malaria test results will be assessed to determine whether criteria for enrollment needs to be adjusted (e.g. representation of likely malaria deaths, rural-urban residence, gender balance, community versus hospital deaths). The CHAMPS site study team (in collaboration with the CHAMPS PO) will analyze the initial data on deaths at each site in order to recommend measures aimed at making deaths selected for MITS as representative as possible within resource constraints, and/or to recommend differential sampling of certain age groups and/or types of deaths in order to optimize the resources allocated for MITS. A similar interim analysis will be conducted after 100 deaths.

Purpose: To identify issues that will affect our approach to the primary analysis. Specifically:

- To assess the distribution of age groups and malaria positivity by different testing methods
- 2. To summarize the amount of missing data for key variables

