- 3. To examine the distributional characteristics of key variables in order to detect potential data entry/reduction errors

Methods: Relevant approaches may include:

- 1. Tabulation of descriptive statistics for key variables including missing observations
- 2. Histograms and other data visualizations

Analysis plan for primary objective

Purpose: To assess the relative contribution of malaria and other infectious disease etiologies to death in adults 18 years and above, in each CHAMPS site

Methods: Relevant approaches may include:

- 1. Descriptive analysis to examine the distribution of deceased cases with malaria, infectious and non-communicable disease etiologies
- 2. Descriptive analysis to examine key demographic and clinical characteristics

8. Data and/or Specimen Banking

CHAMPS datasets captured at each CHAMPS site will be maintained at each site in a local secure data repository as well as mirrored in a secure global data repository maintained by the CHAMPS Project Officer based at Emory University. Any physical data collection instruments containing unique identifiers will be stored in closed, locked filing systems with restricted access at CHAMPS study offices at sites, where each site will be the custodian of their respective site study data. The CHAMPS Network global data repository will be a centralized, web-accessible, composite database of CHAMPS Network data from all participating sites that will provide data visualizations and analyses.

Page 15 of 33 Version: 1.0, 8/22/2022

Where indicated, defined specimens will be shipped to the CHAMPS CPL in Atlanta, Georgia, USA, for confirmatory testing and bio banking. This will be the site for quality assurance and shipment of specimens will be guided by approved material transfer agreements and batch shipment requests, with strict adherence to MoHs and local CHAMPS site regulations on shipment of clinical and research biological specimens.

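### The protocol promises an unequivocal response to an age-patterned malaria finding, but its primary analysis and sample size concern only the all-adult share per site, which age-selective sampling could shift

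*Protocol*

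**What the plan says.** Section 3 (Background, Malaria) reports that in verbal-autopsy studies "malaria appears to be an important contributor to adult mortality (15-20% in some age groups"). The CHAMPS part of the same section says the study will respond unequivocally to this finding, and describes it as a U-"shaped curve, according to age". The next sentence states the aim as "to refute or confirm the hypothesis that malaria is a significant contributor to adult mortality", with no mention of age. The primary objective in Section 2 likewise covers adults of 18 and over.

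Section 7 (Analysis plan for primary objective) gives the purpose as "To assess the relative contribution of malaria and other infectious disease etiologies to death in adults 18 years and above, in each CHAMPS site". Two approaches are listed as possibilities: "Descriptive analysis to examine the distribution of deceased cases with malaria, infectious and non-communicable disease etiologies" and "Descriptive analysis to examine key demographic and clinical characteristics". Neither is said to cross malaria with age.

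Section 7 (Sample size determination) sizes each site for a single proportion with a 5-point margin: 195 deaths at 15%, 138 at 10%. Section 7 (Interim analysis) looks at age groups and malaria positivity after 25-50 deaths, with a similar analysis after 100. It allows the team to "recommend differential sampling of certain age groups and/or types of deaths". No weighting is stated. Section 6 (Mortality Surveillance) says that all notified deaths are tracked and assessed for eligibility, with age as one of the criteria.

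**The concern.** There are two linked problems.

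First, the promise is wider than the stated analysis. The finding to be answered has a shape over age and a size within age groups. A share over all adults is an average across ages and carries no information about that shape. Setting it beside 15-20% in some age groups compares different quantities, and a conclusion in either direction could be wrong.

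Second, the all-adult share depends on the age mix of the deaths sampled. If the interim analysis leads a site to sample some age groups more heavily, the crude share moves although nothing has changed in the population. Sites that choose different mixes would then differ for reasons of design, which undermines the per-location estimates that Section 4 uses to justify the sample size.

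**Working it through.** **Inputs from the protocol.** N = 32,000 adult deaths per year, z = 1.96, d = 0.05, p = 0.15 (respiratory) or 0.10 (lower end of the 10-14% malaria range), and 200-300 deaths per site. The protocol gives no age bands, age-specific shares for its sites or age mix. Those used below are assumptions for illustration.

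**1. The plan's own figures.** n = N z² p(1-p) / ((N-1) d² + z² p(1-p)).
- p = 0.15: z² p(1-p) = 3.8416 × 0.1275 = 0.4898; n = 15,673.7 / (79.9975 + 0.4898) = 194.7, so 195.
- p = 0.10: z² p(1-p) = 3.8416 × 0.09 = 0.3457; n = 11,063.8 / (79.9975 + 0.3457) = 137.7, so 138.

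Both reproduce. Each is the size for one all-adult proportion at one site.

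**2. The average hides the shape.** Four equal age groups at 18, 6, 6 and 18% give (18 + 6 + 6 + 18)/4 = 12%. A flat 12% in every group gives the same figure, and 12% lies inside the protocol's expected 10-14%.

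**3. The crude share moves with the sampled mix.** Assume true shares of 5, 8 and 18% in three bands.
- Mix 40/30/30: 0.4×5 + 0.3×8 + 0.3×18 = 9.8%. At n = 200 the half-width is 1.96 × √(0.098×0.902/200) = 4.1 points.
- Mix 30/20/50: 0.3×5 + 0.2×8 + 0.5×18 = 12.1%.

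The shift is 2.3 points with the same truth. Weighting the second sample back to 40/30/30 restores 9.8%. With 60, 40 and 100 deaths per band, its variance is 0.16×0.0475/60 + 0.09×0.0736/40 + 0.09×0.1476/100 = 0.000425, a half-width of 1.96 × √0.000425 = 4.0 points. In this example reweighting costs no precision.

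**4. Precision by age band.** Half-width 1.96 × √(p(1-p)/m), three equal bands:

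| Deaths | m per band | p = 10% | p = 20% |
|---|---|---|---|
| One site of 200 | 67 | +/-7.2 | +/-9.6 |
| One site of 300 | 100 | +/-5.9 | +/-7.8 |
| Two pooled sites of 200 | 133 | +/-5.1 | +/-6.8 |

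By the protocol's formula, holding +/-5 points in every band needs 195 deaths per band at 15% and 244 at 20%. For three bands that is 585 to 732 per site.

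**5. Contrast between two age groups.** Take 10% against 20%, two-sided 5%, with four equal groups at one site of 200 (m = 50). Power = Φ((0.10 - 1.96 √(2×0.15×0.85/50)) / √((0.09 + 0.16)/50)) = Φ((0.10 - 0.1400)/0.0707) = Φ(-0.565), about 29%. At 300 per site (m = 75) it is about 40%.

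**The case against.** A reader might infer that the primary analysis fails to test the study's own hypothesis. The documents do not support that. The hypothesis sentence in Section 3, the primary objective and the primary purpose are all worded for adults as a whole, and they agree with one another. The age pattern is background to the hypothesis.

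A reader might also infer that the plan restricts itself to one number per site. It does not. The listed methods are only possibilities, demographic description is among them, and the interim analysis examines age groups expressly to inform the primary analysis. A separate analysis plan could tabulate malaria by age. The absence of named bands is therefore not itself the fault.

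Nor does the protocol set a threshold at which the claim counts as refuted. An all-adult result of 9.8% +/-4.1 (5.7 to 13.9%) covers most of the protocol's expected 10-14%, so it should not be presented as a refutation that the plan would declare.

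The 2.3-point shift is smaller than the sampling error at one site. That is true, but the shift is a bias. It does not shrink with more deaths, and it can differ between sites. Differential sampling is also only something the interim may recommend, so the bias is conditional on its being adopted.

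Finally, age bands at one site cannot settle the age question. The figures above confirm this, and it is a reason to limit the promise.

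**Conclusion.** The point holds in a limited form. The all-adult share per site answers the all-adult hypothesis and should stay. It cannot confirm or refute the U shape or the 15-20% figure, so the promise of an unequivocal response reaches beyond what Section 7 defines and is sized for. Section 7 also permits age-selective sampling without stating how the primary share would be corrected, and in the illustration this moves the share by 2.3 points. That the average cannot show an age pattern does not depend on the numbers chosen. The size of the shift and the band precision do depend on the assumed bands, shares and mixes. This is worth correcting, at little cost; it does not invalidate the primary analysis.

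**What to change.** 1. Keep the all-adult malaria share per site as the primary quantity. State that if sampling differs by age, it will be weighted or standardised to the age distribution of all eligible notified deaths at that site. If types of death are sampled differently, include them in the weights.
2. Add the malaria share by age band with 95% confidence intervals, pooled with site as a stratum and shown per site descriptively. Fix the bands before any further interim look at age and malaria positivity.
3. Compare only these age-specific results with the age-specific verbal-autopsy figures, and limit the promise of an unequivocal response to the all-adult share.
4. Confirm that the tracking log keeps age for every eligible notified death. Section 20 bars collecting any data when all parts of the study are declined, and this must be squared with Section 6.

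The cost is a little analysis and a wording change, with no added enrolment. The downside is wide band intervals, which should be stated in advance.

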Background*: Describe the relevant prior experience and gaps in current knowledge. Describe any relevant preliminary data. Provide the scientific or scholarly background for, the rationale for, and significance of the research based on the existing literature and how will it add to existing knowledge	☐ Yes
Study Endpoints*: Describe the primary and secondary study endpoints. Describe any primary or secondary safety endpoints.	☐ Yes
Study Intervention/Investigational Agent*: Describe the study intervention and/or investigational agent (e.g., drug, device) that is being evaluated.	☐ Yes
Drug/Device Handling: If the research involves drugs or devices, describe your plans to store, handle, and administer those drugs or devices so that they will be used only on participants and be used only by authorized investigators. If using a drug, explain if the control of the drug is managed by IDS (or VA/Grady/CHOA research pharmacies). If not, provide IDS exemption document. If a device, explain how the device is being stored and managed.	□Yes
If the drug is under an FDA REMS , plan to complete the REMS checklist found here, on the IRB website.	☐ Yes
If the drug is considered a controlled substance, make sure you have filled out this form.	☐ Yes
If applicable, identify the holder of the IND/IDE/Abbreviated IDE. An Emory investigator who holds an IND or IDE is considered to be a Sponsor-Investigator (S-I). If the study is under an S-I, review this section of our website for additional requirements.	☐ Yes
Procedures involved* : Describe and explain the study design and include a study schema. Describe all research procedures being performed and when they are performed, including procedures being performed to monitor participants for safety or minimize risks	☐ Yes

Page 24 of 33 Version: 1.0, 8/22/2022

Procedures-Minimizing risk*: describe the procedures performed to lessen the probability or magnitude of risks.	□ Yes
Procedures- Drug/Device Use: describe all drugs and devices used in the research and the purpose of their use and their regulatory approval status	☐ Yes
Procedures-Source Records*: describe source records that will be used to collect data about participants. Attach all surveys, scripts, and data collection forms to the submission.	☐ Yes
Procedures-Data collection*: describe what data will be collected during the study and how that data will be obtained	☐ Yes
Procedures- Long Term Follow Up*: once all research-related procedures are complete, what data will be collected during this period. If no data is collected after procedures are completed, please state in the submission.	☐ Yes
Data and Specimen Banking: describe where the specimens will be stored, how long they will be stored, how the specimens will be accessed, and who will have access to the specimens. Depending on the volume and nature of the collection, this may require a separate repository-specific IRB submission. The VA Data Repository SOP is required if the study is creating a data repository at the Atlanta VA. List the data to be stored or associated with each specimen. Describe the procedures to release data or specimens, including the process to request a release, approvals required for release, who can obtain data or specimens, and the data to be provided with specimens.	□Yes
Sharing of Results with Participants*: Describe whether results (study results or individual subject results, such as results of investigational diagnostic tests, genetic tests, or incidental findings) will be shared with participants or others (e.g., the participant's primary care physicians) and if so, describe how the results will be shared If applicable (e.g. for studies involving scans and/or panels of exploratory testing on specimens) Plan for managing the types of findings that might arise. This should include any secondary findings that are being sought actively, findings that might be anticipatable, and findings that might be un-anticipatable. Plan for recognizing, analyzing, and handling incidental findings and how incidental findings will be communicated to participants during the consent process. If the plan is not to disclose any findings, then this should be included. This plan might include the option for participants to opt-out of receiving incidental findings. Description of the research team's responsibilities following disclosure of a finding. This should detail educational information about the nature of the finding, how to seek care	☐ Yes

Page 25 of 33 IRB Form BIO 01192022

from a clinician or specialist, obtaining health insurance to secure treatment, and/or referral to a clinical specialist, if one is required. Reminder to include language in the consent form to let the participants know your plans for this – see Modular Language for Informed Consent Forms on IRB website)	
Study timelines*: describe the duration of an individual participant's participation in the study; anticipated time to enroll all study participants and the estimated date for the investigators to complete this study (complete primary analyses)	☐ Yes
Inclusion and Exclusion Criteria*: describe how individuals will be screened for eligibility and the criteria that define who will be included or excluded in your final study sample	☐ Yes
Population*: describe the study population and indicate specifically whether you will include or exclude each of the following special populations:	☐ Yes
 Adults unable to consent Individuals who are not yet adults (infants, children, teenagers) Pregnant women Prisoners 	
Note: you cannot exclude people with limited English proficiency unless you can demonstrate the scientific need for such exclusion. Community Participation: For studies aimed at addressing issues that affect a certain community or group: How, if at all, will this study involve people from the target community in the design of the study? Conduct of the study? How will the results of the research be shared with the participants and/or the target community/ies?	
If studying Race or Ethnicity, have you defined these terms, and explained their proposed mechanism of action if these characteristics will be used in an explanatory model?	
Research with pregnant women, fetuses, or neonates: review this checklist to verify you have provided enough information to ensure the safety and well-being of this population.	☐ Yes
Research with neonates of uncertain viability: review this checklist to verify you have provided enough information to ensure the safety and well-being of this population.	☐ Yes
Research involving prisoners: review this checklist to verify you have provided enough information to ensure the safety and well-being of this population.	☐ Yes

Page 26 of 33 Version: 1.0, 8/22/2022

Research involving children: review this checklist to verify you have provided enough information to ensure the safety and well-being of this population.	☐ Yes
Research involving cognitively impaired adults: review this checklist to verify you have provided enough information to ensure the safety and well-being of this population.	☐ Yes
Research involving economically or educationally disadvantaged persons: describe the additional safeguards that have been included in the study to protect the rights and welfare of these subjects	☐ Yes
Local Number of Participants*: Indicate the total number of participants to be accrued locally. If applicable, distinguish between the number of participants who are expected to be enrolled and screened, and the number of participants needed to complete the research procedures (i.e., numbers of participants excluding screen failures.) Provide your projected enrolling goals, including the percentage of participants according to sex and race.	☐ Yes
Recruitment Methods*: Describe when, where, and how potential participants will be recruited. Describe the source of participants. Describe the methods that will be used to identify potential participants. Describe materials that will be used to recruit participants. Attach copies of these documents with the application. If including advertisements, attach the final copy of them. When advertisements are taped for broadcast, attach the final audio/videotape. You may submit the wording of the advertisement before taping to preclude re-taping because of inappropriate wording, provided the IRB reviews the final audio/videotape. Describe the amount and timing of any payments to participants. Reimbursement for expenses/travel? If using contests or raffles as incentive, you must offer entry to all potential participants, not just those who enroll in the study/complete study-related procedures, per Georgia State Law. All research recruitment through social media needs to follow this guidance, which does not allow the use of personal social media accounts for some recruitment activities.	□Yes
Withdrawal of Participants*: Describe anticipated circumstances under which participants will be withdrawn from the research without their consent. Describe any procedures for orderly termination. Describe procedures that will be followed when participants withdraw from the research, including partial withdrawal from procedures with continued data collection.	☐ Yes
Risk to Participants*: List the reasonably foreseeable risks, discomforts, hazards, or inconveniences to the participants related to the participant's participation in the research.	☐ Yes

Page 27 of 33 IRB Form BIO 01192022

Include as may be useful for the IRB's consideration, a description of the probability, magnitude, duration, and reversibility of the risks. Consider physical, psychological, social, legal, and economic risks. If applicable, indicate which procedures may have risks to the participants that are currently	
unforeseeable. If applicable, indicate which procedures may have risks to an embryo or fetus should the subject be or become pregnant. If applicable, describe risks to others who are not participants.	
Potential Benefits to Participants*: Describe the potential benefits that individual participants may experience from taking part in the research. Include as may be useful for the IRB's consideration, the probability, magnitude, and duration of the potential benefits. Indicate if there is no direct benefit. Do not include benefits to society or others.	☐ Yes
Compensation to Participants*: Describe if/how subjects will be compensated for participation in this study. Indicate what method compensation will be delivered (e.g. cash, gift card, school credit). Describe the amount and timing of any payments to participants. How much? What kind? Is tax information required? (if so, must be reflected in the informed consent form). Will payments be pro-rated if a participant withdraws early?	☐ Yes
Data Management and Confidentiality*: Describe the data analysis plan, including any statistical procedures or power analysis. Describe the steps that will be taken to secure the data (e.g., training, authorization of access, password protection, encryption, physical controls, certificates of confidentiality, and separation of identifiers and data) during storage, use, and transmission. Describe any procedures that will be used for the quality control of collected data.	☐ Yes
Describe how data or specimens will be handled study-wide*: What information will be included in that data or associated with the specimens?	☐ Yes
 Where and how data or specimens will be stored? How long the data or specimens will be stored? Who will have access to the data or specimens? Who is responsible for receipt or transmission of the data or specimens? How data or specimens will be transported? 	
Data Monitoring and Participants Safety (if this study is more than minimal risk, this section is required):	☐ Yes
Ensure that you review our Data and Safety Monitoring plan guidance for specific details about this section, and examples of what the IRB will be requiring according to the level of risk.	

Page 28 of 33 IRB Form BIO 01192022 If a DSMB is needed, please describe the composition of the board (if not already detailed in the protocol). Review this guidance for more information. If the sponsor protocol does not contain all required information, please in this section.

Describe the plan to periodically monitor the data at the site level according to risk level. Include the appropriate completed monitoring table, if applicable.

Description of the plan for notifying the IRB of reportable events, whether the sponsor requires reporting above and beyond the Emory IRB reporting requirements, and if so, a description of the requirements and plan for meeting them.

Please address the specific details below. If deemed not applicable, please provide rationale:

Subject safety:

- Specific subject safety parameters
- Frequency of subject safety observations
- Individual responsible for safety monitoring
- Subject stopping rules under what conditions will a subject be removed from study participation and who will make the decision?
- Study stopping rules under what conditions will the study be modified or stopped and who will make the decision?
- Reporting mechanisms (i.e. Deviations, adverse events, UPs)

Data Integrity:

- Specific data elements to be reviewed
- Frequency of monitoring data, points in time, or after a specific number of participants
- Individual responsible for data monitoring

Additional considerations for FDA regulated trials

Depending on the procedures affecting risks to participants, the site monitoring plan should specify:

- Categorization of activities done centrally and those on-site if applicable
- Monitoring methods (may include centralized/remote, on-site, and self-monitoring)

- Reference to any tools used (i.e. checklists)
- Identification of events that may trigger changes
- Identification of deviations or failures that would be critical to study integrity

Provisions to Protect the Privacy Interests of Participants*:	☐ Yes
Describe the steps that will be taken to protect participants' privacy interests. "Privacy interest" refers to a person's desire to place limits on whom they interact with or whom they provide personal information.	
 Describe what steps you will take to make the participants feel at ease with the research situation in terms of the questions being asked and the procedures being performed. "At ease" does not refer to physical discomfort, but the sense of intrusiveness a participant might experience in response to questions, examinations, and procedures. 	
 Indicate how the research team is permitted to access any sources of information about the participants. 	
Economic Burden to Participants*: Describe any costs that participants may be responsible for because of participation in the research.	☐ Yes
Consent Process*: Describe where the consent process will take place, any waiting period available between informing the prospective subject and obtaining the consent; and the process to ensure ongoing consent. Describe the role of the individuals listed in the application as being involved in the consent process; the time that will be devoted to the consent discussion; steps that will be taken to minimize the possibility of coercion or undue influence; and steps that will be taken to ensure the participants' understanding. Note: If you are planning to obtain consent via electronic signature, please review this document. Additional guidance on consent documentation and process can be found on our website, under the consent toolkit.	□ Yes
Consent Process-Non-English-Speaking Participants*: Indicate what language(s) other than English are understood by prospective participants or representatives. If participants who do not speak English will be enrolled, describe the process to ensure that the oral and written information provided to those participants will be in that language. Indicate the language that will be used by those obtaining consent. If you checked N/A, please provide reasoning of why subjects with limited English proficiency are excluded. Note: if you stated that subjects with LEP will be enrolled, you are approved for the use of the Emory IRB short forms. Please read the guidance about the use of short forms here.	☐ Yes

Consent Process-Children: After determining if the subject is a child per GA law (or if enrolled outside GA, per state/country law), please describe whether parental permission will be obtained from:	☐ Yes
Both parents unless one parent is deceased, unknown, incompetent, or not reasonably available, or when only one parent has legal responsibility for the care and custody of the child.	
 One parent even if the other parent is alive, known, competent, reasonably available, and shares legal responsibility for the care and custody of the child. 	
Describe whether permission will be obtained from individuals other than parents, and if so, who will be allowed to provide permission. Describe the process used to determine these individuals' authority to consent to each child's general medical care.	
When assent of children is obtained describe whether and how it will be documented per Emory Policies and Procedures	
Consent Process-Cognitively Impaired Adults: describe the process to determine whether an individual is capable of consent. The IRB allows the person obtaining assent to document assent on the consent document and does not routinely require assent documents and does not routinely require children to sign assent documents.	□ Yes
Consent Process-Adults Unable to Consent: List the individuals from whom permission will be obtained in the order of priority. (E.g., durable power of attorney for health care, a court-appointed guardian for health care decisions, spouse, and adult child.) For research conducted in the state, review "46 LEGALLY AUTHORIZED REPRESENTATIVES AND SURROGATE CONSENT" to be aware of which individuals in the state meet the definition of "legally authorized representative." For research conducted outside of the state, provide information that describes which individuals are authorized under applicable law to consent on behalf of a prospective subject to their participation in the procedure(s) involved in this research. Describe the process for the assent of the participants. Indicate whether:	□Yes
 Assent will be required of all, some, or none of the participants. If some, indicated, which participants will be required to assent and which will not. 	
If assent will not be obtained from some or all participants, an explanation of why not.	
Describe whether the assent of the participants will be documented and the process to document assent. The IRB allows the person obtaining assent to document assent on the	

consent document and does not routinely require assent documents and does not routinely require participants to sign assent documents	
Waiver or Alteration of Consent Process (consent will not be obtained, required information will not be disclosed, or the research involves deception) Review the Emory IRB waiver document to ensure you have provided sufficient information for the IRB to make these determinations. If the research involves a waiver of the consent process for planned emergency research, please review the "CHECKLIST: Waiver of Consent for Emergency Research (HRP-419)" to ensure you have provided sufficient information for the IRB to make these determinations.	□Yes
Setting*: Describe the sites or locations where your research team will conduct the research including where the subject will be identified and recruited, where the research procedures will be performed, and if you will involve a community advisory board. For research conducted outside the organization and its affiliates describe the site-specific regulations or customs affecting the research outside the organization and the local scientific and ethical review structure outside the organization.	☐ Yes
Resources Available*: Describe the resources available to conduct the research such us the feasibility of recruiting the required number of suitable participants within the agreed recruitment period; describe the time that you will devote to conducting and completing the research; describe the availability of medical or psychological resources that participants might need as a result of an anticipated consequences of the human research; describe your process to ensure that all persons assisting with the research are adequately informed about the protocol, the research procedures, and their duties and functions.	□Yes
Multi-Site Research when Emory is the Lead Site: Study -Wide Number of Participants: indicate the total number of participants to be accrued across all sites. Study-Wide Recruitment Methods: If this is a multicenter study and participants will be recruited by methods not under the control of the local site (e.g., call centers, national advertisements) describe those methods. Describe when, where, and how potential participants will be recruited. Describe the methods that will be used to identify potential participants. Describe materials that will be used to recruit participants. Describe the processes to ensure communication among sites. See "WORKSHEET: Communication and Responsibilities (HRP-830)." All sites have the most current version of the protocol, consent document, and HIPAA authorization. All required approvals (initial, continuing review and modifications) have been obtained at each site (including approval by the site's IRB of record). All modifications have been communicated to sites and approved (including approval by the site's IRB of record) before the modification is implemented.	☐ Yes

Page 32 of 33 IRB Form BIO 01192022 All engaged participating sites will safeguard data, including secure transmission of data, as required by local information security policies.

All local site investigators conduct the study in accordance with applicable federal regulations and local laws.

All non-compliance with the study protocol or applicable requirements will reported in accordance with local policy

Describe the method for communicating to engaged participating sites (see "WORKSHEET: Communication and Responsibilities (HRP-830)"):

- Problems (inclusive of reportable events).
- Interim results.
- The closure of a study

If this is a multicenter study where you are a participating site/investigator, describe the local procedures for maintenance of confidentiality. (See "WORKSHEET: Communication and Responsibilities (HRP-830).")

- Where and how data or specimens will be stored locally?
- How long the data or specimens will be stored locally?
- Who will have access to the data or specimens locally?
- Who is responsible for receipt or transmission of the data or specimens locally?
- How data and specimens will be transported locally?

30. Appendices

